12.7.3.1 Programming MRI Protection Mode

Prior to undergoing an MR scan, the ImageReady System must be programmed to the MRI Protection Mode using the PRM. The PRM is to be kept ON and in MRI Zone I or II as close to the MRI room as possible.

WARNING: The PRM is MR Unsafe and must remain outside the MRI site Zone III (and higher) as defined by the American College of Radiology Guidance Document for Safe MR Practices¹¹. Under no circumstances should the PRM be brought into the MRI scanner room, (Zone IV), or the control room (Zone III). Programming the PG to MRI Protection Mode should be done as close to the planned start of the MR scan as possible.

1. Start monitoring the subject as outlined in section 12.7.3.3
2. Program the MRI Protection Time-out (nominal setting: 6 hours; programmable values are OFF, 3, 6, 9, 12 hours)

¹⁰ Wolf SM LF, Nelson CA, Kahn JP, Cho MK, Clayton EW, et al. Managing incidental findings in human subjects research: Analysis and recommendations. *J Law Med Ethics*. 2008;36:219

¹¹ Kanal E, et al., *American Journal of Roentgenology* 188:1447-74, 2007.

3. Program the PG to the MRI Protection Mode
4. Print the MRI Protection Settings Report. This report documents the MRI Protection Mode settings and details.
 - a. If the Time-out feature is used, the report includes the exact time and date when MRI Protection Mode will expire. If the Time-out feature is used, the MRI technologist/radiologist must verify that adequate time remains to complete the scan and to exit the MR scanner room.

Please refer to the *BSC MRI Technical Guide* for more information regarding PG MRI Protection Mode programming and other associated MRI warnings, cautions, and potential adverse events.

12.7.3.2 Heart Rhythm Monitoring after MRI protection mode programming

It is **required** that the heart rhythm be monitored by the site Principal Investigator or a sub-investigator for all subjects after programming MRI protection mode ON and prior to initiation of the MR Scan.

- Monitor the heart rhythm for at least 5 minutes using the monitoring equipment screen. Heart rate and any abnormal rhythms, including incidence of ectopy shall be documented.
 - In particular, look for signs of progressive AV nodal block over time, permanent or intermittent complete AV block, or trifascicular block (alternating bundle branch block or PR > 200 ms with LBBB or other bifascicular block) or a sinus pause > 2s during this time period. **Any** occurrence of these events will disqualify subjects from undergoing the MRI.
 - For such subjects, MRI protection mode must be turned OFF. These subjects should be withdrawn from the study.

12.7.3.3 Monitoring of Subjects during the MRI Protection Mode

Subjects must be continuously monitored by the site Principal Investigator or a sub-investigator for the entire duration in which the PG is in MRI Protection Mode. All subject monitoring must be documented (visual and auditory cues are acceptable when the subject is being connected to the equipment defined below).

For the entire duration that the PG is in MRI Protection Mode, the following will be performed:

1. Investigational centers must utilize continuous monitoring of all of the following
 - a. ECG (minimum of a 3-lead ECG is required)
 - b. Pulse oximetry with waveform monitoring (non-impedance based Finger plethysmography)
 - c. Blood pressure

NOTE: Both the ECG and pulse oximeter alarms should be turned to the ON position on the monitoring machine for the entire duration of the MR scan.

2. Ensure that an external defibrillator and medical personnel trained in external defibrillation and cardiopulmonary resuscitation (CPR) are present
3. Subjects must be continuously monitored by the site Principal Investigator or a sub-investigator trained in monitoring hemodynamic stability using ECG, pulse oximetry and blood pressure, along with maintaining normal voice and visual contact.
4. In addition, **for the entire duration of the MR scan**, the following will be performed:
 - a. The heart rate, blood pressure and oxygen saturation levels will be documented in 5 ± 2 minutes intervals.
 - b. ECG and pulse oximeter alarms must be ON
 - c. It is recommended that a rhythm strip is printed at each interval.
 - d. If there are any abnormal rhythms, a rhythm strip to document the abnormal rhythm should be printed if possible.

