5.1.1 MRI Protection Mode

MRI Protection Mode is accessible through the 3120 programmer/recorder/monitor (PRM) that has the 2868 software application (see Section 5.5). Prior to the patient undergoing an MRI scan, the PG must be programmed to the MRI Protection Mode using the PRM.

Adherence to the MRI Conditions of Use must be verified prior to each scan to assess the patient's eligibility and readiness for an MR scan (see Section 6).

At the start of the study, in international geographies, the 'MRI Protection Mode' will have CE mark and be available for commercial use.

In the US, a programmer key (dongle) is required to interrogate the VR ICDs and CRT-Ds to access the investigational 'MRI Protection Mode'.

NOTE: MRI Protection Mode may become approved in the US during the study. If this occurs, then the dongle will no longer be needed to access MRI Protection Mode.

In the MRI Protection Mode, the following features and functions are suspended:

- Bradycardia sensing/pacing
- Cardiac Resynchronization Therapy
- Tachycardia detection and therapy
- PaceSafe™** automatic threshold(s)
- Daily diagnostics (Lead Impedance, Intrinsic Amplitude, Pace Threshold)
- Motion and respiratory sensors
- Magnet detection
- RF telemetry
- Battery voltage monitoring
- Beeper is disabled

** Only available internationally outside the US

NOTE: In MRI Protection Mode there is no pacing and no antitachycardia therapy available.

During MRI Protection Mode, the patient will not receive pacing until the PG is returned back to normal operation. Additionally, the system will not detect ventricular arrhythmias and the patient will not receive anti-tachycardia pacing (ATP) or shock defibrillation therapy until the pulse generator is programmed back to normal operation.

Refer to the *BSC ImageReady MR Conditional Defibrillation System MRI Technical Guide*², here to forward referred to as the *BSC MRI Technical Guide*, for additional information regarding MRI Protection Mode.

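### Section 12.7.3.3 requires ECG and pulse oximeter alarms only during the MR scan, although pacing and tachycardia therapy are off for all of MRI Protection Mode

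*Combined protocol and SAP*

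**What the plan says.** Section 12.7.3.3 sets two tiers of monitoring.

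- **Whole mode.** The first tier opens with "For the entire duration that the PG is in MRI Protection Mode, the following will be performed". It requires continuous ECG, pulse oximetry with waveform and blood pressure, an external defibrillator with trained personnel, and an investigator or sub-investigator in voice and visual contact.
- **Scan only.** Item 4 adds further requirements for the duration of the MR scan, among them item 4b: "ECG and pulse oximeter alarms must be ON".

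The NOTE under item 1 sits inside the whole-mode list, but its own words limit it to the scan: "ECG and pulse oximeter alarms should be turned to the ON position on the monitoring machine for the entire duration of the MR scan". The NOTE uses *should* and item 4b uses *must*; the period is the same in both. No other visible section mentions monitor alarms. Conditions of Use 6.1 (item 4) and 6.2 (item 6) require continuous ECG and oximetry throughout the mode, without reference to alarms.

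On device therapy, section 5.1.1 states: "In MRI Protection Mode there is no pacing and no antitachycardia therapy available".

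**The concern.** The alarm requirement follows the scanner, while the hazard follows the device mode. From programming until exit, the device would not treat a pause, AV block or a ventricular arrhythmia. Detection then depends on the people watching and on the monitoring equipment. The protocol backs up the observer with alarms during the scan but does not ask for the same back-up in the rest of the mode.

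Those other periods include moving the subject. The programmer must stay out of Zones III and IV (12.7.3.1, 12.7.3.5), and leaving the mode by programmer needs the wand. Each scanned subject therefore enters the mode outside the scanner room, goes in, comes out and is reprogrammed outside. At stake is subject safety in a short window, not the validity of any analysis.

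**Working it through.** No figure in the plan needs reproducing and no formula is tested. The check sets the period covered by the alarm rule against the period without device therapy.

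| Stage | Device therapy | Attended monitoring required | Alarms required |
|---|---|---|---|
| Programming to start of scan | Off (5.1.1) | Yes (6.1 item 4; 12.7.3.2; 12.7.3.3) | No |
| MR scan | Off | Yes (12.7.3.3) | Yes (NOTE; item 4b) |
| End of scan to exit from the mode | Off | Yes (12.7.3.3) | No |

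**Before the scan.** Section 12.7.3.2 applies after the mode is switched on and before the scan starts. It instructs: "Monitor the heart rhythm for at least 5 minutes using the monitoring equipment screen". This stage therefore lasts at least 5 minutes in every scanned subject. If the check finds a disqualifying rhythm, no scan follows: "For such subjects, MRI protection mode must be turned OFF". The alarm rule then never applies to that subject, although an investigator is watching the screen at the time.

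**After the scan.** Section 12.7.3.5 directs that the device be programmed out when the scan is complete and recommends doing so as soon as possible. It gives no maximum.

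**Length of the gap.** Time in the mode without an alarm requirement = (programming to scan start) + (scan end to exit) ≥ 5 minutes + *t*, where *t* is the post-scan interval, with no limit stated. Section 13.2.7 will summarise both intervals descriptively, so the plan recognises them, but the documents contain no observed values.

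**Boundary of the scan.** *MR scan* is not defined for monitoring purposes. Section 12.7.3.4 records one initiation time and one completion time. Section 28.1 separates about 30 minutes of imaging from about one hour in the bore. The exact edges are therefore uncertain, but the 5-minute lower bound does not depend on them, because 12.7.3.2 places the check before the scan is initiated.

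**The case against.** The strongest reply is that the two tiers look deliberate. Item 4 is introduced as an addition for the scan. In the rest of the mode an investigator attends continuously with ECG, oximetry, blood pressure and a defibrillator, and in the pre-scan check the required task is to watch the screen. Section 12.7.3.1 asks for programming close to scan start and keeps the programmer on and nearby. Exclusion criteria 5 to 7 and the VVI 40 check in 12.7.2.3, where one paced beat disqualifies, remove many subjects at risk of pauses or AV block. All of this stands and makes the gain small. It does not remove the point: the same attended monitoring applies during the scan, and alarms are still required there. The documents give no reason for dropping them while therapy remains off.

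Two stronger readings are tempting, and the documents support neither.

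- **A conflict over timed records.** Item 4a limits these to the scan: "The heart rate, blood pressure and oxygen saturation levels will be documented in 5 ± 2 minutes intervals". Table 12-6 lists the same records under the stage when the device is in MRI Protection Mode, so a reader might infer contradictory recording periods. That row also holds scan-only items such as scanner model, sequence durations and scan start and stop times. It reads as a filing category by stage of visit, and the heading is at most ambiguous.
- **A gap of hours.** The Time-out settings in 12.7.3.1 ("nominal setting: 6 hours; programmable values are OFF, 3, 6, 9, 12 hours") might suggest this. They limit how long the device can stay in the mode. They say nothing about the interval between scan end and exit, which 12.7.3.5 directs to be prompt.

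**Conclusion.** The point holds as a small, optional safety improvement. The written alarm requirement leaves out at least 5 minutes before the scan and an unstated time after it, while device therapy is off. What is missing is alarm back-up only; subjects are not unmonitored, and the protocol does not forbid alarms outside the scan. No endpoint, sample size or analysis is affected.

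Section 12.12 applies the same visit flow to medically necessary scans, where a trained health care professional may take the investigator's monitoring role, so the alarm wording carries over to those visits.

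Confidence is medium. The text is clear, but the MRI Technical Guide must also be satisfied (section 6) and is not available. If it already requires alarms throughout the mode, the change only brings the protocol into line with it.

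**What to change.** - In the NOTE under item 1 of 12.7.3.3, change the period from the MR scan to the whole time the pulse generator is in MRI Protection Mode.
- Move item 4b into the whole-mode list, with alarms on once the subject is connected to the monitor. This respects the existing allowance for visual and auditory cues during connection and avoids technical deviations.
- Leave items 4a, 4c and 4d and Table 12-6 unchanged. Item 4c depends on the intervals in 4a, so they should stay together.

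The cost is a wording change, on monitors that 12.7.3.1 already requires to be in use when the mode is programmed, plus some nuisance alarms while the subject is moved.

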12.7.3.4 MR Scan Sequences Protocol

Refer to Table 28-1 in Section 28 for the MR Scan Sequences Protocol.

The following data is required to be collected:

1. Medications used for sedation in the MR scanner, if applicable
2. MR Scanner manufacturer and model
3. Time of MR scan initiation
4. Time duration for each sequence within the RF intensive and Gradient intensive scans
5. Total duration of RF intensive scan sequences
6. Total duration of Gradient intensive scan sequences
7. Time of MR scan completion

12.7.3.5 Exiting the MRI Protection Mode

Upon completion of the MR scan, program the PG out of the MRI Protection Mode by interrogating the device using the wand (RF telemetry is disabled in MRI Protection Mode). It is recommended to program the PG out of MRI Protection Mode as close to the end of MR scan as possible.

- Document the Time of exiting MRI Protection Mode.

Note: The PRM is MR Unsafe and must remain outside the MRI site Zone III (and higher). Under no circumstances should the PRM be brought into the MRI scanner room, the control room, or the MRI site Zone III or IV areas.

Upon exiting the MRI Protection Mode, all parameters are restored to pre-MRI Protection Mode values with two exceptions:

- Restoration of function of the Minute Ventilation¹² (MV) sensor is delayed. If MV was programmed to ON or Passive at the time of entry into MRI Protection Mode, upon exit from the mode, an automatic six hour calibration of the sensor will begin. MV-driven rate response is not available during this calibration period. If MV-driven rate response is desired sooner, a manual calibration can be performed.
- The Beeper will remain OFF upon exiting MRI Protection Mode.

12.7.4 Device Evaluation after the MR Scan

1. All implanted leads will be evaluated within two hours upon exit from the MRI Protection Mode through the implanted PG **for THREE separate consecutive sets of measurements** using the test parameters listed in Table 12-3:
 - Manual pacing threshold tests, as defined in sections 12.5.1.1, 12.5.1.2 and 12.5.1.3. Sensing amplitude
 - Impedance
 - Shock impedance (RV lead only)
2. Test for phrenic nerve stimulation (PNS) and measure the PNS threshold if detected in the programmed LV lead configuration
3. Perform an assessment of Beeper function as defined in section 12.7.1.1. After performing the assessment of the Beeper, if the Beeper is audible, the user may choose to manually re-enable the Beeper.

Record the measurements in the EDC system.

12.7.5 Completing the MRI Visit

1. The PG data must be reviewed to document whether any episodes of polymorphic or monomorphic VT or VF that required ATP or shock therapy are present, following the MR scan.
 - a. If polymorphic or monomorphic VT or VF episodes are present:
 - i. Print the 'Arrhythmia Logbook' and 'Selected Episodes Report' (counters and EGMs) using the PRM
 - ii. A copy of the Selected Episode Report(s) with counters and EGMs is expected to be submitted to Boston Scientific **within 5 business days** using the upload tool in the EDC system

¹² Only available internationally outside the US

- iii. If a physical copy of the Selected Episode Report(s) is to be submitted (instead of an electronic upload), the copy is expected to be submitted to the ECG Core Lab **within 5 business days**
 2. Program the device according to physician discretion, and indicate if any permanent device programming was changed
 3. Print the ‘Quick Notes’ Report
 4. Perform a Save All:
 - a. Save device data to a USB using the programmer “Save All” feature
 - b. Label the USB with the subject ID#, Date, and “MRI”
 - c. Retain the original USB at the center, and a copy is expected to be submitted to Boston Scientific **within 5 business days** using the upload tool in the EDC system
 - i. If a physical copy of the USB is to be submitted (instead of an electronic upload) use a PC to make the copy and label it the same way as the original. **Do not make a copy by using the programmer a second time as this will create a new USB with slightly different information**
 5. Schedule the MRI+1 month follow-up visit.

12.7.6 MRI Visit Source Data Requirements

Source data requirements at the MRI Visit are described in Table 12-6:

Table 12-6: MRI Visit Source Documentation Requirements

Source Documentation Requirement	Disposition
Pre-MR scan: 
 • Assessment of patient history of unexplained syncope • Device Evaluation (pace threshold, sense amplitude, impedance, RV shock impedance, LV Phrenic Stimulation threshold) • PRM ECG strips from manual threshold tests documenting LOC for all implanted leads • Assessment of Beeper function • Printout of ‘Quick Notes’ Report • Cardiology and Radiology MRI Conditions of Use are satisfied • 12 leads ECG & 10s rhythm strip (either from the ECG machine or the BSC PRM) 	Retain at center
While PG is programmed to MRI Protection Mode: 
 • MRI Protection Settings Report • Heart rate, blood pressure, Oxygen saturation levels, and Voice Contact in 5 ± 2 minute intervals 	Retain at center

Source Documentation Requirement	Disposition

 • Rhythm strip every 5 ± 2 minutes (recommended) • Rhythm strips for abnormal rhythms, as applicable (recommended) • Medications used for sedation in the MR scanner, if applicable • MR Scanner manufacturer and model • Time of MR scan initiation • Time duration for each sequence within the RF intensive and Gradient intensive scans • Total duration of RF intensive scan sequences • Total duration of Gradient intensive scan sequences • Time of MR scan completion 	
When PG is programmed out of MRI Protection Mode: 
 • Time of exiting MRI Protection Mode 	Retain at center
Post-MR scan: 
 • Device Evaluation (pace threshold, sense amplitude, impedance, RV shock impedance, LV Phrenic Stimulation threshold) • PRM ECG strips from manual threshold tests documenting LOC for all implanted leads • Assessment of Beeper function • Document if polymorphic or monomorphic VT/VF episodes requiring therapy, are present • Documentation of spontaneous VT/VF episode(s) by PRM strips, as applicable: 
 ○ ‘Selected Episodes Report’ (counters and EGMs required) ○ ‘Arrhythmia Logbook’ • Printout of ‘Quick Notes’ Report 	Retain at center
Adverse Events	Retain at center
MR scanner DICOM dump/ report file including items such as scan sequence settings and durations as well as calculated scan metrics such as whole body average SAR. The DICOM file must contain both images and scan sequence data.	Retain the original at the center and submit a copy to Boston Scientific
Save All	Retain the original at the center and submit a copy to Boston Scientific

12.8 MRI + 1 Month Visit (Phase I only)

The MRI + 1 Month Visit must be performed as a clinic visit and will occur at 30 ± 7 days after the MRI Visit.

12.8.1 Device Evaluation

1. All implanted leads will be evaluated through the implanted PG for **THREE separate consecutive sets of measurements** using the test parameters listed in Table 12-3:
 - Manual pacing threshold tests, as defined in sections 12.5.1.1, 12.5.1.2 and 12.5.1.3.
 - Sensing amplitude
 - Impedance
 - Shock impedance (RV lead only)
2. Test for phrenic nerve stimulation (PNS) and measure the PNS threshold if detected in the programmed LV lead configuration

Record the measurements in the EDC system.

12.8.2 VF Induction

Subjects who successfully complete the study required MRI scan and either qualify for the “for-cause” VF induction or consented to be part of the VF induction Sub-study will undergo a VF Induction.

“For cause” VF induction is required if the below criteria are met at the MRI + 1 Month Visit:

- A reduction in the RV lead R-wave amplitude of $> 50\%$ post-MRI, as measured at the MRI + 1 Month Visit compared to the pre MRI value collected during the MRI Visit, with a RV lead R wave that is greater than or equal to 5 mV post-MRI as measured during the MRI + 1 Month Visit

“For cause” VF inductions are ideally performed at the MRI + 1 Month Visit, but may be performed up to 14 calendar days after the MRI + 1 Month Visit.

Subjects will be assessed for clinical stability prior to performing the VF induction testing (both those subjects who qualify for the “for-cause induction and those who are part of the VF induction Sub-study), per physician discretion. The following criteria should be considered prior to performing VF Induction testing:

1. Unstable heart failure requiring hospitalization in the last 30 calendar days
2. Unable to tolerate sedation (e.g. IV sedation, general anesthesia)
3. Planned cardiac revascularization procedure

4. Evidence of lead fracture or lead dislodgment
5. Evidence of PG malfunction (i.e. error code)
6. Right Ventricular Lead R wave is less than 5 mV

Subjects determined to be clinically stable will undergo VF Induction testing according to the following procedure:

1. Subjects will undergo IV sedation or general anesthesia, according to local standard of care for VF induction testing.
2. Program the following settings:
 - 1-Zone, VF
 - Rate = 180 bpm or less. Lower than 180 bpm may be appropriate based on patient's previous history, per physician's discretion
 - Sensitivity: 0.6 mV or less (more sensitive – 0.15 to 0.6 mV)
3. Perform the VF induction test through the implanted ICD/CRT-D through the *EP Tests* screen
4. Select the VF Induction method at the discretion of the physician (e.g. 50 Hz Manual Burst, Shock on T, V Fib, etc.)
 - a. Begin printing a real-time ECG and electrograms with markers prior to starting the induction
 - b. Initiate the VF induction testing
 - c. If an arrhythmia is induced and the device has not started charging after 16 seconds, then the physician may choose to apply therapy through alternative methods; e.g. Stat Shock or external defibrillation
 - d. Upon rhythm termination, stop the ECG and electrograms
5. If the first induction attempt induces monomorphic or polymorphic VT; or the VF spontaneously terminates prior to charging
 - a. Treat as needed
 - b. Attempt second VF induction using a different induction method or induction parameters (e.g. Shock on T with different Shock Coupling, Fib High longer duration etc.) A maximum of two VF induction attempts is allowed per subject. A VF Induction attempt is defined as an attempt to induce VF that results in an episode entry in the Arrhythmia Logbook, i.e. NSVT, VF/VT that spontaneously terminates.
6. Upload into the EDC all induced episodes **within 5 business days**

- a. If a physical copy of induced episode(s) is to be submitted (instead of an electronic upload), the copy is expected to be submitted to the ECG Core Lab **within 5 business days**

When the VF Induction testing is complete, program the device, per physician discretion.

When 25 VF episodes in 25 subjects post MRI scan are confirmed (combination of spontaneous VF episodes, “for-cause” and VF Induction Sub-study VF episodes) by the ECG Core Lab, sites will be notified by BSC to stop all VF induction testing. This includes “for-cause” inductions, and VF Induction Sub-study inductions that were planned but not yet completed.

